12.1. Communication of issues

In the event of any prohibition or restriction imposed (e.g., clinical hold) by an applicable Competent Authority in any area of the world, or if the investigator is aware of any new information which might influence the evaluation of the benefits and risks of Genotropin, Pfizer should be informed immediately.

In addition, the investigator will inform Pfizer immediately of any urgent safety measures taken by the investigator to protect the study patients against any immediate hazard, and of any serious breaches of this NI study protocol that the investigator becomes aware of.

14. LIST OF TABLES

Table 1. Variables to be captured in SWEGHO.

15. LIST OF FIGURES

None

ANNEX 1. LIST OF STAND-ALONE DOCUMENTS

None

ANNEX 2. KIMS ETIOLOGY CLASSIFICATION LIST

Idiopathic

1.1 Idiopathic GHD

Congenital

Genetic cause of GHD

- 2.1.1.1 GH-gene-defect (Type 1A dominant or recessive)
- 2.1.1.2 GH gene-defect (specify)
- 2.1.1.3 GHRH gene-defect (specify)
- 2.1.1.9 Other genetic cause of GHD (specify)

Central malformation

- 2.1.2.1 Septo-optic dysplasia
- 2.1.2.2 Empty sella syndrome (including pituitary aplasia)
- 2.1.2.3 Solitary central maxillary incisor syndrome
- 2.1.2.4 Mid-line palatal cleft
- 2.1.2.5 Arachnoid cyst
- 2.1.2.6 Congenital hydrocephalus
- 2.1.2.9 Other central malformation (specify)

Complex syndrome with congenital GHD

- 2.1.3.1 Fanconi pancytopenia
- 2.1.3.2 Rieger syndrome
- 2.1.3.3 EEC syndrome (Ectrodactyly-Ectodermal Dysplasia-Clefting syndrome)
- 2.1.3.9 Other complex syndrome with congenital GHD (specify)

Prenatal infection

- 2.1.4.1 Rubella
- 2.1.4.9 Other than rubella prenatal infection (specify)

Bio-inactive GH syndrome

- 2.1.5.1 Kowarski type
- 2.1.5.9 Other than Kowarski type bio-inactive GH syndrome (specify)

Functional GHD

- 2.1.6.1 GH-receptor defect (Laron Type)
- 2.1.6.2 GH-receptor/postreceptor defect (specify)
- 2.1.6.3 IGF resistance (specify)
- 2.1.6.9 Other functional GHD (specify)

2.1.9 Congenital unknown

Acquired

Tumors of the pituitary/hypothalamic area

- 2.2.1.1 Craniopharyngioma
- 2.2.1.2 Germ cell tumours (specify: dysgerminoma, pinealoma)
- 2.2.1.3 Hamartoma

Adenoma

- 2.2.1.4.1 Non-secreting (non-functioning pituitary adenoma - NFPA)
- 2.2.1.4.2 ACTH (Cushing disease)
- 2.2.1.4.3 GH (acromegaly)
- 2.2.1.4.4 Prolactin (prolactinoma)
- 2.2.1.4.5 Gonadotropin
- 2.2.1.4.6 TSH
- 2.2.1.4.7 Co-secreting (specify)
- 2.2.1.4.9 Other adenoma (specify)
- 2.2.1.5 Cyst (specify: Rathke's, epidermoid, dermoid)
- 2.2.1.6 Glioma
- 2.2.1.7 Meningioma

- 2.2.1.8 Schwannoma
- 2.2.1.10 Chordoma
- 2.2.1.11 Primary pituitary carcinoma
- 2.2.1.12 Sarcoma
- 2.2.1.13 Metastatic carcinoma
- 2.2.1.14 Hematologic metastases
- 2.2.1.9 Other tumors of pituitary/hypothalamic (specify)

Cranial tumors distant from the pituitary/hypothalamic area

- 2.2.2.1 Astrocytoma
- 2.2.2.2 Ependymoma
- 2.2.2.3 Glioma
- 2.2.2.4 Medulloblastoma
- 2.2.2.5 Nasopharyngeal tumour
- 2.2.2.9 Other cranial tumors distant from the pituitary/hypothalamic area (specify)

Treatment for malignancy outside the cranium

Leukemia

- 2.2.3.1.1 Lymphatic leukemia
- 2.2.3.1.2 Myeloid leukemia
- 2.2.3.1.3 Aplastic leukemia
- 2.2.3.1.9 Other leukemia (specify)

Lymphoma

- 2.2.3.2.1 Hodgkin lymphoma
- 2.2.3.2.2 Non-Hodgkin lymphoma
- 2.2.3.2.9 Other lymphoma (specify)

Solid tumor

- 2.2.3.3 Solid tumor (specify)

Other causes of acquired GHD

Head trauma/ injury

- 2.2.4.1.1 Perinatal head trauma
- 2.2.4.1.2 Traumatic brain injury
- 2.2.4.2 CNS infection (specify: meningitis, encephalitis, septic cavernous sinus)
- 2.2.4.3 Hydrocephalus
- 2.2.4.4 Granulomatous diseases (specify: sarcoidosis, tuberculosis, syphilis, fungal)
- 2.2.4.5 Langerhans cell histiocytosis (histiocytosis X, eosinophilic granuloma Hand-Schüller-Christian disease)

Vascular system

- 2.2.4.6.1 Infarction (apoplexy)
- 2.2.4.6.2 Postpartum necrosis (Sheehan syndrome)
- 2.2.4.6.4 Aneurysm
- 2.2.4.6.5 Sickle cell anemia
- 2.2.4.6.6 Thalassaemia
- 2.2.4.6.7 Subarachnoid hemorrhage
- 2.2.4.6.9 Other vascular (specify)
- 2.2.4.7 Lymphocytic hypophysitis
- 2.2.4.8 Hemochromatosis
- 2.2.4.9 Other (specify)

## 1 AMENDMENTS FROM PREVIOUS VERSION(S)

Not applicable, first version.

## 2 INTRODUCTION

KIMS® (Pfizer International Metabolic Database) a non-interventional study sponsored by Pfizer, was run between 1994 and 2012. It evaluated the long-term safety and treatment outcomes of adult patients treated with Genotropin in a real-world clinical setting. As such, KIMS® was particularly well-suited to capture information regarding rare adverse events and atypical treatment reactions, on the one hand, and information on treatment outcomes that allowed for cost effective, individualized GH treatment.

Patients are treated with GH over a long time period, usually over several years and for some patients the treatment duration can even be life-long. In order to strengthen the data collected in KIMS®, this study-SWEGHO- is designed to further follow up long-term Genotropin therapy treatment outcomes in a real-world clinical setting and to be able to compare patients who started treatment after 2012 with patients who started treatment in 1990-ies.

This Statistical Analysis Plan (SAP) provides detailed methodology for summary and statistical analyses of data of the planned statistical evaluation of Pfizer study “SWEGHO - A PROSPECTIVE NON INTERVENTIONAL STUDY PROTOCOL WITH PRIMARY DATA COLLECTION - ASSESSMENT OF THE LONG TERM TREATMENT OUTCOMES OF GENOTROPIN TREATMENT IN GHD PATIENTS IN SWEDEN (A628 somatropin)”.

This SAP version 1.0 was written with access to only a small sample of patients (without access to the complete study database).

### 2.1 STUDY DESIGN

This study is as a prospective national, multi-center, non-interventional, descriptive study open to adult hypopituitary patients with GHD who are treated with Genotropin as prescribed in clinical practice.

This non-interventional study does not include pre-specified endpoints, but collects information from adult subjects prescribed Genotropin in clinical practice.

#### Study population

At the time of the final version 1.0 of the SAP around 340 patienter are included in the study. The study population consists of;

Patients 18 years of age and above who are prescribed Genotropin and who are either;

- a) Newly diagnosed with GHD

- b) Diagnosed with GHD before 2013 and previously treated with Genotropin and followed in KIMS®
- c) Transition patients diagnosed with CO-GHD before 2013

More details regarding the including inclusion and exclusion criteria, can be found in the Study Protocol, A6281313 NON-INTERVENTIONAL STUDY PROTOCOL Amendment 5, 23 October 2015 (1).

## 2.2 STUDY OBJECTIVES

The overall purpose of this study is:

- 1) To assess the long term treatment outcomes of GH treatment in patients who are prescribed and treated with Genotropin.

CCI

## 3 ANALYSIS SETS/POPULATIONS

### 3.1 FULL ANALYSIS SET

The full analysis population (FAS) will consist of all correctly enrolled patients who received at least one dose of Genotropin. Erroneously enrolled patients are excluded from FAS since these patients did not meet the inclusion criteria or meet an exclusion criterion (which was discovered after enrollment to the study).

### 3.2 SAFETY ANALYSIS SET

The safety analysis includes all enrolled patients received at least one dose of Genotropin. Erroneously enrolled patients are included in the safety analysis set.

### 3.3 SUBGROUPS

- Adult patient of 18 years of age and above and diagnosed with Childhood onset GHD, labeled Childhood onset GHD (CO-GHD)
- Adult patient of 18 years of age and above, not in the CO-GHD group above and diagnosed with GHD before 2013 and previously treated with Genotropin and followed in KIMS®, labeled KIMS GHD (*K-AO-GHD*)
- Adult patient of 18 years of age and above, not in the CO-GHD group above and newly diagnose with GHD, labeled *Naïve-AO-GHD* (N-AO-GHD)

#### 4 ENDPOINTS AND COVARIATES

The patient is treated according to clinical practice. Normal clinical practice may include routine diagnostic procedures such as; blood samples, CTs, MRI and other tests. The decision of what measures to perform is not pre-specified in the protocol but is based on the clinical experience, standards and judgment of the investigator. Data from patient records, which align with the data to be collected in the database eCRF as specified in the study protocol, is collected and entered into the database. The data is collected during the patients' routine visits to the clinic.

Endpoints will be summarized at baseline and at follow up and change from baseline will be derived if appropriate.

Continuous data will be summarized using descriptive statistics where the following parameters will be reported:

- Number of observations (n),
- Mean,
- Quartile 1 (Q1),
- Median,
- Quartile 3 (Q3),
- Standard deviation (SD),
- Range (Min,Max)

Categorical data will be presented as the number and percentage of patients.

In general, all data will be listed. Summary tables will be structured with a column for each of the three subgroups defined in Section 3.3 and a column for the total if other not stated.

The following variables should be captured according to the Study Protocol (if available):

Variable	Role	Data source(s)	
Informed Consent (mandatory)	Before Baseline	Personally signed and dated Informed Consent Document	
BACKGROUND INFORMATION -Age -Gender - Ethnic origin (only CRF) -Age at menarche	Baseline		

-Menopause/Amenorre -Age at Menopause/Amenorrea -Puberty (Induced, Spontaneous) -Age at end of growth			
MEDICAL HISTORY -Hypertension -Claudication -Coronary Heart Disease -Stroke -Arthrosis -Diabetes -Type I -Type II -Epilepsy -Neoplasm -Other Significant disease -Fractures	Baseline	Patient record and or CRF	
FAMILY HISTORY -Diabetes -Cardiovascular Disease -Hip Fracture -Colon Polyps -Colon Cancer -Neoplasm (other)	Baseline	Patient record and or CRF	
PITUITARY DISEASE -Date of Diagnose -Childhood onset -Brain Tumor -Visual Field deficit -Ophthalmoplegia -Tumor treatment -Tumor Size -Tumor type	Baseline	Patient record and or CRF	
DIAGNOSE OF GHD -Date of Diagnose of GHD -Test method -Date of test	Baseline	Patient record and or CRF	
BASELINE PREVIOUS GH TREATMENT -Treatment start date -Treatment stop date	Baseline	Patient record and or CRF	

EXAMINATION -Weight -Height -BMI -Blood pressure -Heart rate (Supine) -CT/MRI -Waiste, Hip -Body Composition -Additional Hormone Abnormalities	Baseline, Follow up visit	Patient record	
TREATMENT -GH treatment -Concomitant Medication of special interest	Baseline, Follow up visit	Patient record	
LABORATORY -Glucose -HbA1c -IGF-I	Baseline, Follow up visit	Patient record	
ADVERSE EVENT	Follow up visit	Patient record and information obtained from the patient	

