Start of data collection is planned to October 2013, end of data collection October 2018. Final study report is planned to October 2019.

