9.13. Analysis of safety

Safety outcomes of long-term Genotropin therapy are analyzed to provide information as requested. Frequency and incidence rates of AEs are calculated and compared to data on general populations, when available. Incidence and frequency rates of AEs are also compared between different subgroups in the study.

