## 4.3 SAFETY ENDPOINTS

For each patient, the safety event reporting period begins at the time of the patient’s first dose of Genotropin® or the time of the patient’s informed consent if s/he is already exposed to Genotropin®, and lasts through the end of the observation period of the study, which must include at least 28 calendar days following the last administration of a drug under study. Most often, the date of informed consent is the same as the date of enrollment. In some situations, there may be a lag between the dates of informed consent and enrollment. In these instances, if a patient provides informed consent but is never enrolled in the study (e.g., patient changes his/her mind about participation), the reporting period ends on the date of the decision to not enroll the patient.

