### 4.3.1 Adverse Events

Definitions for the different types of AE including the definition for Serious Adverse Events (SAEs) are given in the study protocol.

The following variables has been collected for each AE and SAE; a diagnosis is preferred as event term rather than only describing symptoms, the date when the AE started and stopped, whether the AE is serious or not, causality assessment, action taken with regard to Genotropin®, AE caused patient to discontinue study and outcome.

All AEs will be classified by System Organ Class (SOC) and Preferred Term (PT) according to the available MedDRA Version.

The seriousness criterion will also be listed for SAEs.

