**4.4 OTHER ENDPOINTS/ASSESSMENTS**

Detailed operational definitions for some endpoints/assessments are give below.

Age is defined as age at baseline.

Duration of study will be summarized by subgroup. Duration of study is defined as time from baseline to exit date.

CCI [Redacted]

[Redacted]

[Redacted]

CCI [Redacted]

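### The protocol promises AE incidence rates compared between subgroups, but the readable SAP gives only percentages of patients, which can mislead if follow-up differs

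*SAP*

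**What the plan says.** Protocol 9.13 makes two commitments on AEs: "Frequency and incidence rates of AEs are calculated and compared to data on general populations, when available", and "Incidence and frequency rates of AEs are also compared between different subgroups in the study". Protocol 9.12 leaves the detailed methods to the SAP, and the SAP introduction says that it supplies them.

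The readable SAP text that bears on AEs is this:

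- **SAP 4.3** defines each patient's safety reporting period. It starts at first dose, or at consent for a patient already exposed, and "lasts through the end of the observation period of the study, which must include at least 28 calendar days following the last administration".
- **SAP 4.3.1** lists the variables collected for each AE, including start and stop dates, and says "All AEs will be classified by System Organ Class (SOC) and Preferred Term (PT) according to the available MedDRA Version". It names no summary measure.
- **SAP 4** gives the general rule: "Categorical data will be presented as the number and percentage of patients". It adds the layout: "Summary tables will be structured with a column for each of the three subgroups defined in Section 3.3 and a column for the total".
- **SAP 4.4** has study duration summarised by subgroup: "Duration of study is defined as time from baseline to exit date". It does not link duration to AEs.
- **SAP 6.1** rules out hypothesis tests and urges caution because there is no comparator arm.

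**The concern.** The protocol distinguishes frequency from incidence. Number and percentage of patients delivers the first but not the second, because nothing in the readable SAP turns time at risk into a denominator.

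This matters because the AE tables set three subgroups side by side: childhood-onset GHD (CO-GHD), adult-onset patients carried over from KIMS (K-AO-GHD) and newly diagnosed adult-onset patients (N-AO-GHD). The longer a group is watched, the larger the share of it with at least one event. If the groups are watched for different lengths of time, the columns can differ when the rates are equal, or agree when the rates differ. The caution in SAP 6.1 is about the missing comparator arm and does not warn of this.

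The design makes unequal follow-up plausible. The protocol abstract states "Start of data collection is planned to October 2013, end of data collection October 2018", so a later entrant has less time before the planned end. Protocol 9.2 leaves length of participation to investigator and patient. KIMS patients already existed when the study opened, whereas newly diagnosed patients become available only as they are diagnosed.

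**Working it through.** **The plan's own figures.** The only planning number is the expected enrolment in Protocol 9.10: 600 + 250 + 50 = 900, which reproduces. The documents give no AE rate, entry pattern or follow-up by subgroup, so what follows is a range under stated assumptions.

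**Inputs**

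- Data collection from October 2013 to October 2018, 5 years (Protocol 6).
- Constant event rate r per person-year, the same in both adult-onset groups unless stated (assumed).
- No withdrawal (assumed).
- N-AO-GHD patients enter evenly over the 5 years, so follow-up is uniform from 0 to 5 years (assumed).
- K-AO-GHD patients enter evenly over 5, 3 or 2 years, or all at the start (assumed). Follow-up is then uniform on 0–5, 2–5 or 3–5 years, or fixed at 5 years.

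**Formulas.** The expected share with at least one event is

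- follow-up uniform on a to b years: 1 − [exp(−ra) − exp(−rb)] / [r(b − a)]
- fixed 5 years: 1 − exp(−5r)

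**Equal true rates, r = 0.10.** N-AO-GHD: 1 − (1 − exp(−0.5))/0.5 = 21.3%.

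| K-AO-GHD entry | K-AO-GHD % | Ratio K to N |
|---|---|---|
| evenly over 5 years | 21.3 | 1.00 |
| over first 3 years | 29.3 | 1.37 |
| over first 2 years | 32.9 | 1.54 |
| all followed 5 years | 39.3 | 1.85 |

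The true rate ratio is 1.00 in every row.

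**Other rates, K-AO-GHD entry over 2 years**

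- r = 0.01: 3.92% / 2.46% = 1.59
- r = 0.05: 18.1% / 11.5% = 1.57
- r = 0.20: 54.8% / 36.8% = 1.49

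The distortion depends little on the assumed rate and strongly on the assumed entry pattern.

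**Masking.** Let the true N-AO-GHD rate be double: 0.10 against 0.05. N-AO-GHD shows 21.3%.

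- K-AO-GHD entry over 2 years: 18.1%, so N to K = 21.3/18.1 = 1.18
- K-AO-GHD all followed 5 years: 1 − exp(−0.25) = 22.1%, so N to K = 21.3/22.1 = 0.96

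**Precision of a rate.** SAP 2.1 reports around 340 patients enrolled. Assuming the planned 600:250:50 mix, N-AO-GHD has 340 × 250/900 ≈ 94 patients. With entry even over 5 years:

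- r = 0.01: 94.4 × 0.0246 ≈ 2.3 first events in 232 person-years. With 2 events, the exact Poisson 95% interval is about 0.1 to 3.1 per 100.
- r = 0.10: 94.4 × 0.2131 ≈ 20.1 first events in 201 person-years. With 20 events, it is about 6.1 to 15.4 per 100.

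CO-GHD is not modelled.

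**The case against.** The other side has several fair points.

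1. **Duration is reported by subgroup.** A reader would see unequal follow-up and could divide each percentage by mean duration. This recovers much of the picture. With r = 0.10 and all KIMS patients followed 5 years, 39.3/5 = 7.9 against 21.3/2.5 = 8.5 per 100, a ratio of 0.92 instead of 1.85. But it leaves the reader to do the analysis row by row, without intervals and with follow-up not stopped at the first event. It also shows that the data for a proper rate are at hand.
2. **Protocol 9.10 expects each patient to stay for the whole study unless withdrawn.** That points towards common follow-up, but it cannot give a late entrant 5 years before a fixed planned end.
3. **KIMS patients also enter gradually.** They need a new consent (Protocol 9.9), and data come only from routine visits. The all-at-start scenario is therefore an upper bound, and the 1.00 case is possible.
4. **Protocol 9.13 is conditional.** Safety analyses are supplied on request, and the protocol allows more than one SAP. This softens the mismatch. Still, this SAP has a safety set, safety endpoints and subgroup columns, so AE percentages would stand side by side under it.
5. **A rate may be defined elsewhere.** The table shells are in a separate document that was not available, and SAP 4.4 is partly redacted. This stands, and it limits the finding to the readable text. The quoted rule is also a general one, applied to AEs because 4.3.1 offers nothing else.
6. **The study is descriptive.** So is an incidence rate with an interval; it involves no test.

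**Conclusion.** The concern holds, as a change that should be made, with medium confidence. Protocol 9.13 promises AE incidence rates by subgroup, and the readable SAP defines neither the rate nor its denominator, although it defines a reporting period that could serve.

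Under the assumptions above, equal rates of 10 per 100 person-years give a K-AO-GHD to N-AO-GHD ratio of percentages anywhere from 1.00 to 1.85. A true doubling in N-AO-GHD can shrink to 1.18 or appear as 0.96. Actual follow-up by subgroup is not documented, so this is the possible size of the distortion, not a demonstrated one.

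**What to change.** In SAP 4.3.1, and to match in the table shells, specify for AEs and SAEs, overall and by SOC and PT, for each subgroup and the total:

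- the number of patients with a first event;
- person-years at risk within the SAP 4.3 reporting period, censored at the first event;
- incidence per 100 person-years with an exact Poisson 95% confidence interval;
- n (%) alongside, as now planned.

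If incidence rates are instead left to another SAP, or are already in the table plan, say so here and point to the definition.

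The cost is SAP wording and modest programming on dates already collected. No new data are needed, and the no-testing rule is untouched. The downside is wide intervals for rare terms, as the interval of about 0.1 to 3.1 per 100 shows. That is real imprecision, which a bare percentage would not show.

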#### 4.1 BASELINE AND VISIT WINDOW DEFINITION

Baseline is defined as the baseline visit according to the eCRF.

In order to summarize data by year the following visit window definition will be used for follow-up visits:

1. Each visit will be assigned to a yearly measurement according to the principle Year 1 if visit occurred 1 year from baseline visit  $\pm 6$  months. Year 2 if visit occurred 2 year from baseline visit  $\pm 6$  months, and so on. If a patient has more than one visit in a year (as defined here) principle 2 and 3 below will be applied. Visits occurring between baseline visit and baseline visit + 6 months will not be included in summaries by year.
2. Select the visit that has a IGF-1 value.
3. If more than one visit within a year has an IGF-1 value, select the visit with a IGF-1 value closest to the target date. The target date is defined as follows (using Year 1 as an example); Target date for Year 1 is baseline visit plus exactly 12 months (the date occurring 1 year after baseline visit).

The definition of visit windows will be applied in summary tables. Data from all visits will be reported in listings.

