9.2. Setting

Patients previously followed in KIMS[®], new patients fulfilling the inclusion criteria and transition patients with confirmed childhood onset GHD will be asked to participate. All patients should be diagnosed with GHD according to the current medical standards, and treated with Genotropin as prescribed in clinical practice^{4,5}.

After having given their informed consent, the patient is enrolled in the study. The patient is treated according to clinical practice. Normal clinical practice may include routine diagnostic procedures such as; blood samples, CTs, MRI and other tests. The decision of what measures to perform is not pre-specified in the protocol but is based on the clinical experience, standards and judgment of the investigator. Data from patient records, which align with the data to be collected in the database eCRF as specified in this protocol, will be collected and entered into the database. The data will be collected during the patients' routine visits to the clinic.

The interval between each the patient's visits, duration of treatment and participation in the study for each individual are at the discretion of the investigator and the patient.

After informed consent has been obtained from the patient, background data are collected and if available in KIMS[®], all the data will be transferred automatically into the database. This includes but is not limited to medical history, laboratory, imaging and background data such as Genotropin dosing. Background information, includes: history of birth, family and medical history, pituitary diagnosis, growth, puberty, GH treatment before start in the study (if applicable).

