**4.3.2 Vital signs**

Vital signs include weight, height, bmi, blood pressure (systolic and diastolic), heart rate, body composition, CT/MRI (yes/no) and change in hormonal deficiencies.

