## **5 HANDLING OF MISSING VALUES**

Patients with missing values of a particular endpoint will not contribute to the analysis.

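### SAP 4.1 picks one whole visit per yearly window by its IGF-1 value, so another endpoint's value recorded only at an unselected visit drops out of any by-year table

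*SAP*

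**What the plan says.** SAP 4.1 sets out one window rule for summarising follow-up data by year. Each visit goes to the year whose anniversary of baseline lies within ±6 months. If a patient has more than one visit in a window, two further principles apply. The first is "Select the visit that has a IGF-1 value". The second, for windows with several IGF-1 visits, takes the one nearest the target date. On scope, the section says "The definition of visit windows will be applied in summary tables", while listings carry every visit. It also says "Visits occurring between baseline visit and baseline visit + 6 months will not be included in summaries by year".

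SAP section 5 adds "Patients with missing values of a particular endpoint will not contribute to the analysis".

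SAP section 4 describes the output in general terms: "Endpoints will be summarized at baseline and at follow up and change from baseline will be derived if appropriate". The follow-up variables listed there include weight, BMI, blood pressure, waist and hip, body composition, glucose and HbA1c beside IGF-I. SAP 4.3.2 adds items such as "CT/MRI (yes/no) and change in hormonal deficiencies".

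Neither the visit schedule nor the content of a visit is fixed. Protocol 9.2 leaves to investigator and patient "The interval between each the patient's visits, duration of treatment" and length of participation. SAP section 4 says "The decision of what measures to perform is not pre-specified in the protocol".

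**The concern.** The rule is written for all data summarised by year, but it selects on the presence of one laboratory value. Since visits and measurements follow routine care, two visits in the same window need not carry the same measurements. The visit with IGF-1 may lack an HbA1c, glucose, weight or blood pressure value that another visit in that window has. The rule gives no way to use that second value, so the patient leaves the yearly row for that endpoint, and any change from baseline for that year goes too.

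At stake is the n, and with it the summary statistics, of by-year tables for endpoints other than IGF-I. Descriptive summaries are the whole planned output (SAP 6.1 and 6.2). SAP 2.1 gives around 340 patients included when the SAP was finalised, and section 4 splits tables into three subgroup columns plus a total. Avoidable gaps are therefore worth closing, even though no test depends on them.

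**Working it through.** The plan states no figure on this point, so there is nothing to reproduce. The check is a reading of the rules, followed by an illustration on assumed inputs.

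**Reading the rules together**

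1. Selection starts only when a window holds more than one visit. With one visit, nothing is dropped.
2. The unit selected is the visit. The only criteria are presence of IGF-1 and, among IGF-1 visits, distance from the target date.
3. No visible text exempts other endpoints or lets a value come from an unselected visit.
4. Once the selected visit stands for the year, an endpoint absent there is missing, and SAP section 5 takes the patient out for that endpoint.

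**Worked case.** A patient has a visit at month 10 with IGF-1 but no HbA1c, and one at month 13 with HbA1c but no IGF-1. Year 1 runs from month 12 − 6 = 6 to month 12 + 6 = 18, so both visits fall in it. The rule selects month 10. The patient does not contribute to Year 1 HbA1c, although a value exists one month from the target date.

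**Possible size (every input is an assumption).** Take windows with two visits and independent recording. Let a be the chance that the endpoint is recorded at an IGF-1 visit and b the chance at a visit without IGF-1.

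- Exactly one visit has IGF-1: the rule keeps a; filling from the other visit keeps a + (1−a)b. Loss per such window = (1−a)b.
- Both visits have IGF-1: loss per such window = a(1−a).

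To express either as a loss over all patient-years, multiply by the share of patient-years of that kind. With share m for the first kind:

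| m | a | b | loss = m(1−a)b |
|---|---|---|---|
| 0 | any | any | 0 |
| any | 1 | any | 0 |
| 0.10 | 0.9 | 0.5 | 0.10 × 0.05 = 0.5 points |
| 0.25 | 0.9 | 0.5 | 0.25 × 0.05 = 1.25 points |
| 0.5 | 0.8 | 0.5 | 0.5 × 0.10 = 5 points |
| 0.5 | 0.5 | 0.5 | 0.5 × 0.25 = 12.5 points |

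For the second kind, the loss within such a window is 0 at a = 1, 0.9 × 0.1 = 9 points at a = 0.9, and 0.5 × 0.5 = 25 points at a = 0.5. These are per-window figures and cannot be compared with the table until multiplied by the share of such windows, which is also unknown.

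For scale only: if all 340 patients had a visit in a given year's window, 0.5 points is 0.005 × 340 = 1.7 patients and 5 points is 0.05 × 340 = 17 patients.

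**Two wording gaps in the same rule**

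- If several visits in a window all lack IGF-1, neither principle names a visit.
- With ±6 months closed at both ends, a visit at exactly month 18 satisfies Year 1 (12 + 6) and Year 2 (24 − 6). One at exactly month 6 satisfies Year 1 and also touches the period excluded after baseline.

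**The case against.** The strongest reply is that one index visit per patient-year is a coherent convention. It keeps IGF-I, GH dose, weight and laboratory values contemporaneous. Protocol section 8 asks about the relation between clinical status, dosage schedule and response, and IGF-I is the only marker that SAP 4.2 classifies. Anchoring on the IGF-1 visit fits that aim. This stands: a reader might infer that the anchoring is itself an error, and the documents do not support that. The defect is only that nothing is said about endpoints missing at the anchor visit.

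It can also be said that no affected table can be named. SAP section 4 speaks only of baseline and follow-up, the table shells are in a separate TLF plan (SAP section 7), and SAP 4.4, which announces operational definitions, is partly redacted. This stands too. The point is therefore conditional on an endpoint being tabulated by year. It is not a statement that, say, the HbA1c table loses patients.

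Finally, the loss figures rest on assumed visit patterns and independent recording. This is conceded. A reader might take the 9 or 25 points per window as an overall loss, which they are not. A reader might also infer bias in the yearly means. Nothing in the documents shows that values at unselected visits differ systematically from those kept. What remains after these concessions is that the visible text, followed literally, discards a usable value, and that the listings do not restore it to a table's n, mean or median.

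**Conclusion.** The point holds as a minor one. Under SAP 4.1 with section 5, a value of an endpoint other than IGF-I that was recorded only at an unselected visit is lost from any by-year row for that endpoint.

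The size cannot be derived. It is zero where windows hold a single visit or where the endpoint is always recorded at the selected visit. It grows with the share of multi-visit windows and with incomplete recording at the IGF-1 visit. The conclusion rests on the visible rule applying to every endpoint tabulated by year, with no exemption in the TLF plan or the redacted part of SAP 4.4.

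The reach is limited to descriptive yearly tables. No hypothesis test depends on it (SAP 6.1), all visits are listed, and the IGF-I classification in SAP 4.2 is unaffected because it uses any assessment after baseline. The missing rule for windows without IGF-1 and the overlap at exactly 18 months are small wording gaps that add little weight but should be closed in the same edit.

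**What to change.** Amend SAP 4.1 for by-year tables:

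- Keep the IGF-1 visit, as now chosen, as the index visit for the window.
- If an endpoint is missing at the index visit, use the non-missing value in the same window closest to the target date; on a tie, the earlier visit.
- If no visit in the window has IGF-1, apply the same closest non-missing rule to each endpoint.
- Take linked measures from one visit: systolic with diastolic pressure, weight with BMI, waist with hip.
- Keep same-visit values in any table that relates IGF-I to dose or weight.
- Make windows half-open, with target minus 6 months included and target plus 6 months excluded. A visit at exactly month 18 is then Year 2 only, and one at exactly month 6 is Year 1.

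Check the TLF plan and the unredacted SAP 4.4 first. If they already cover this, a cross-reference in 4.1 is enough.

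The cost is SAP wording and simple programming, with no new data. The downside is that some values in a yearly row may come from a different visit than the IGF-I value, which a table footnote should state.
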